Sample Size Justification. The primary outcome for the power analysis is the percentage of time spent in target (70-180mg/dl). We estimate from previous studies^{13,28} that these values may have a standard deviation as high as 25 percentage points, in which case with 100 patients in each group we will have 80% power to detect a difference of 10 percentage points in time in range (e.g., 65 vs. 75); a moderate effect size of 0.4. If the standard deviation is lower (e.g., 15 as has been true in some studies), we will have greater power (99%) to detect a 10 point difference and are still well powered to detect smaller differences (e.g., 90% power for a 7 point difference). All power calculations assume an alpha of 0.05 and minimal statistical effects of clustering within the hospitals (e.g., unit or nurse level).

C. Detailed study procedures

Recruitment: Critical care clinical research coordinators will screen for preliminary eligibility and forward potential participant names to study team using a secure medical record in-basket process. The study team will determine eligibility. The study team will ask for permission for the patient to be approached. If permission is granted, the study team will verify eligibility and obtain informed consent from the patient or the patient's legally authorized representative. Consent will be obtained prior to research participation and CGM placement. Recruitment is expected at a rate of 5 patients per week over seven months. Our target recruitment will be 100 MICU patients.

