Procedures. Glucose data will be directly transferred from the MICU patients (N=100) to Android mobile phones/Dexcom G6 app which captures and stores glucose values every 5 minutes (up to 288 values/day for 100% CGM wear). CGM data is automatically transferred from phones/Dexcom G6 app to Dexcom Clarity. Individual patient discrete data will be downloads directly from the Clarity site. Historical controls meeting the gateway criteria (glucose >250 mg/dl or on IV insulin during admission) from the same MICU will be matched on the following factors: Diagnosis and type of diabetes, home insulin use, steroid use during hospitalization, vasopressor use, North vs. South MICU wings (NP team floor vs. resident team floor, respectively), and diabetic ketoacidosis (DKA)/hyperosmolar hyperglycemic syndrome (HHS) status. POC glucose values for historical controls (N=100) will be obtained directly from OSUWMC EHR. EHR data will be obtained through an information warehouse request providing time stamped, POC glucose value for each match patient. All data will be uploaded into STATA 15.0 where it will be cleaned and merged prior to analysis.

Variables and Measures. Demographic, admission, and diabetes specific variables of interest appear in Table 2 and will be collected from the EHR for MICU participants and for historical controls. Clinical condition variables will include presence of renal replacement, mechanical ventilation, ECMO, associated cardiac arrest or cerebrovascular accident and SOFA score. SOFA score was calculated, though noted to have limited discriminant function for predicting mortality.³² The SOFA score has been validated in critically ill patients³³, and is currently the scoring system recommended by the Sepsis 3 definition.³⁴ CGM and POC glucose data will be aggregated into glucose ranges and thresholds as described in Table 2.

Exploratory aim:

RQ 4: To assess hospitalization outcomes and conduct economic evaluation of the costs to deliver CGM implementation in the MICU.

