		Proportion of patients approached to received GCM monitoring/number of patients eligible to receive initial CGM monitoring	Admission		
		Acceptability of CGM			
		Appropriateness of CGM			
		Feasibility of CGM			
		CGM knowledge			
Aim 3	Patient condition	Demographic data: Age, race/ethnicity, gender	Admission	
 • EHR 	
		Height, weight, and BMI	Admission		
		Diagnosis and type of diabetes	Admission		
		Home diabetes regimen	Admission		
		Total daily insulin dose	Daily		
		Past medical history: tobacco use, COPD, hypertension, heart failure, coronary artery disease	Admission		
		Clinical condition: Admission/inpatient glucose, HbA1c, admission diagnosis, admitting service, MICU	Admission		

		location (North vs. South), DKA/HHS, sepsis, acute liver failure, acute heart failure		
		Clinical condition: SOFA score, dialysis, thromboembolic events, ECMO mechanical ventilation, ICU/hospital length of stay, cardiac arrest, cerebrovascular accident, mortality	Daily	
		Medications: vasopressor use, steroids, anticoagulants, acetaminophen dose	Daily	
		Creatinine, eGFR, ALT, AST, TBR, WBC, procalcitonin, ferritin, CRP, IL6, D-dimer, PTT, INR, troponin, pH, BHB, bicarbonate	Daily	
		Enteral or parenteral nutrition	Daily	
		O2 sat, pAO2, blood pressure	Daily	
Aim 3	Glycemic control	Time in target for CGM patients (70-180mg/dl)	Daily	
 • Clarity • EHR
		Time 100-180mg/dl for CGM patients	Daily	
		Time 140-180mg/dl for CGM patients	Daily	
		Time above range for CGM patients (>180mg/dl & >250mg/dl)	Daily	
		Time in hypoglycemia for CGM patients (<70mg/dl & <55mg/dl)	Daily	
		Percent POC in target (70-180mg/dl) (matched controls)	Daily	
		Percent POC 100-180mg/dl (matched controls)	Daily	
		Percent POC 140-180mg/dl (matched controls)	Daily	
		Percent POC above range (>180mg/dl & >250mg/dl) (matched controls)	Daily	
		Percent POC in hypoglycemia (<70mg/dl & <55mg/dl) (matched controls)	Daily	
		Glucose standard deviation	Daily	
		Glucose coefficient of variation	Daily	
Aim 4	Hospitalization outcomes and costs	Length of stay [ICU, total stay]	Discharge	
 • EHR • Clarity download
		Cost of stay	Discharge	
		Discharge level of care [home, SNF]	Discharge	
		Morbidity	Discharge	
		Mortality	Discharge	
		Readmission rate [30 days]	30d s/p discharge	
		Cost of CGM vs. standard POC glucose monitoring materials.	Discharge	

Table 3. Nurse Participant Schedule of Activities

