Descriptive statistics of central tendency (range, mean, median, and standard deviation) will describe variable characteristics and examine data distribution for normality and outliers. Descriptive statistics will summarize the sample characteristics and distribution of each variable. Data will be screened for normality, outliers, and homogeneity. Continuous variables with normal distribution will be reported as mean (standard deviation) while non-normal distribution will be reported as median (interquartile range). For **RQ1**, multivariate linear models will be used to evaluate clinical utility and implementation variables while examining the effects of patient condition (i.e., sequential organ failure assessment (SOFA) score, renal replacement, ventilator support, pH) as covariates. For **RQ 2**, For qualitative analysis of focus group data, a code book will be developed a priori based on the semi-structured interview questions. Interview data, fieldnotes and memos were imported into NVivo 12.0 (Doncaster, Australia) for data management and analyzed using a qualitative descriptive approach.^{35,36} Two researchers ([name] and [name]) will perform qualitative analysis. Portions of text will be coded with terms that were low inference (“data close”); then grouped into thematic categories and subthemes.³⁵ For **RQ3**, hyperglycemic and hypoglycemic events will be identified for CGM and non-CGM users. Discrete CGM glucose values will be used to aggregate derived measures of glucose variability, including time in target (blood glucose value of 70-180mg/dl), time 100-180mg/dl (representing a more conservative target used inpatient), time 140-180mg/dl (representing institutions IV insulin guideline glycemic target), time above target (>180mg/dl & >250mg/dl), time in hypoglycemia (<70mg/dl & <55mg/dl), glucose standard deviation, and coefficient of variation. Daily percent time in target as well as cumulative time in target will be assessed. Time in target will be derived from ADA glucose targets defining hypoglycemia as a blood glucose less than 70mg/dl and peak post-prandial glucose as <180mg/dl³⁷. The blood glucose range of 70-180mg/dl is consistent with other studies examining time in target.³⁸⁻⁴¹ Measures of hypoglycemia will be in accordance with ADA recommendations for measurement at <70mg/dl and <55mg/dl which is a marker of severe hypoglycemia.⁴² Days with $\geq 70\%$ CGM percent wear, as recommended by ADA, will be included in daily time in target analysis.⁴² For matched historical control patients, percent POC in target (70-180mg/dl), 100-180mg/dl, 140-180mg/dl, percent POC >180mg/dl and percent POC >250mg/dl, percent POC <70mg/dl and percent POC <55mg/dl will be evaluated consistent with other recent studies.^{43,44} For CGM daily glycemic control (i.e., time in range [70-180mg/dl], time 100-180mg/dl, time 140-180mg/dl), linear mixed effect modeling (LMM) for repeated measures will be used to adjust for between subject and within subject variance. A 3-tiered LMM will be used to control for patient, unit, and nurse specific variability. LMM will be repeated for analysis of daily POC glucose control for matched historical control patients for days with ≥ 3 POC fingersticks performed. Two-sided significance level of 0.05 was used for all the statistical tests. For **RQ4**, the cost analysis for the proposed study will be conducted from the provider perspective. Cost estimation involves three major steps: (1) identify the relevant cost items; (2) measure the use of resources; and (3) place a value on the resources used. We will obtain estimated costs for proposed CGM implementation. Direct benefits and savings tend to fall into one of two categories: either savings from enhanced efficiency and productivity, or savings from outcomes improvement (e.g., reducing length of stay, lower 30 day readmissions). Costs that do not vary with the number of patients will be categorized as fixed costs, whereas those that vary by the number of patients will be defined as variable costs. The costs of the CGM implementation will be compared to costs under a control scenario. We will estimate the potential costs and cost savings resulting from the CGM implementation.

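### The RQ3 comparison names no CGM-versus-control term and no adjustment for starting glycemia, so an imbalance left after matching could pass as a CGM effect

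*Combined protocol and SAP*

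**What the plan says.** **Model (III.D Data Analysis, RQ3).** For daily glycemic control in CGM patients, "linear mixed effect modeling (LMM) for repeated measures will be used to adjust for between subject and within subject variance". The model has three tiers (patient, unit, nurse). It is then repeated for the matched controls on days with at least three POC readings. No fixed-effect covariate is named, and no term compares CGM with control. For RQ1, the same section does name covariates: SOFA score, renal replacement, ventilator support and pH.

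**Matching (III.C, RQ 3 Procedures).** Controls are matched on "Diagnosis and type of diabetes, home insulin use, steroid use during hospitalization, vasopressor use", MICU wing, and DKA/HHS status. They must have had glucose above 250 mg/dl or IV insulin during the admission. No HbA1c or glucose value is a matching factor.

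**Data collected.** Table 2 (Patient Participant Schedule of Activities, Aim 3) has an admission row that begins "Clinical condition: Admission/inpatient glucose, HbA1c, admission diagnosis, admitting service, MICU". The RQ 3 Variables and Measures paragraph says that the Table 2 variables are taken from the EHR for participants and historical controls alike.

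**Power (III.B, Sample Size Justification).** "The primary outcome for the power analysis is the percentage of time spent in target (70-180mg/dl"). The plan assumes that "these values may have a standard deviation as high as 25 percentage points", and states that "with 100 patients in each group we will have 80% power to detect a difference of 10 percentage points in time in range". At an SD of 15 it states that "we will have greater power (99%) to detect a 10 point difference", and gives "90% power for a 7 point difference".

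**The concern.** Starting glycemia plausibly predicts later time in range. In a randomised trial, leaving it out would mainly cost precision. Here the controls are historical, so nothing beyond the six matching factors and the shared entry criteria balances it.

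Those criteria do not fix the starting level. One route is glucose above 250 mg/dl with no upper limit, and the other is IV insulin at any glucose. The timing also differs: participants qualify on current IV insulin, controls on IV insulin at some time during admission.

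A patient random effect absorbs between-patient variance. It does not remove a difference in mean starting glycemia between the groups. If the groups differ, part of the estimated difference reflects where patients began. If adjustment is decided only after the data are seen, the choice of covariates is open to the result.

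**Working it through.** **Inputs from the documents:** SD 25 (also 15), 100 per group, difference 10 points (also 7), two-sided alpha 0.05.

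**Assumptions, since the documents give neither:** r, the correlation of starting glycemia with time in range, from 0.2 to 0.5; and g, the group difference in starting glycemia in SD units, from 0.1 to 0.3. Both mean what is left after matching.

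**1. The plan's own power.** SE = SD × √(2/100). At SD 25, SE = 25 × 0.1414 = 3.54. Power = Φ(10/3.54 − 1.96) = 80.7% (80.4% by the t-test), against 80% stated. At SD 15, power is 99.7% for 10 points and 91.0% for 7 points, against 99% and 90% stated. The stated figures reproduce.

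**2. Precision.** Residual SD = SD × √(1 − r²). At SD 25, for a 10-point difference:

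| r | Residual SD | SE | Power | n per group for 80% |
|---|---|---|---|---|
| 0 | 25.00 | 3.54 | 80.7% | 99 |
| 0.2 | 24.49 | 3.46 | 82.3% | 95 |
| 0.3 | 23.85 | 3.37 | 84.3% | 90 |
| 0.4 | 22.91 | 3.24 | 87.0% | 83 |
| 0.5 | 21.65 | 3.06 | 90.4% | 74 |

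These rows assume no baseline imbalance. With imbalance g, the adjusted variance is multiplied by about 1 + g²/4. At g = 0.3 that is 1 + 0.09/4 = 1.0225, or about 1% on the SE, so the gain is then slightly smaller.

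**3. Bias without adjustment.** Bias = r × g × SD. Type I error is the chance of a significant result when CGM has no effect and the estimate is shifted by this amount: 1 − Φ(1.96 − bias/3.54) + Φ(−1.96 − bias/3.54). At SD 25, bias in points (type I error):

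| r | g = 0.1 | g = 0.2 | g = 0.3 |
|---|---|---|---|
| 0.2 | 0.50 (5.2%) | 1.00 (5.9%) | 1.50 (7.1%) |
| 0.3 | 0.75 (5.5%) | 1.50 (7.1%) | 2.25 (9.8%) |
| 0.4 | 1.00 (5.9%) | 2.00 (8.7%) | 3.00 (13.6%) |
| 0.5 | 1.25 (6.4%) | 2.50 (10.9%) | 3.75 (18.6%) |

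The bias is 5% to 38% of the 10-point target difference. It can run in either direction, depending on which group starts higher.

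**The case against.** Several objections carry weight.

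- **Silence is not exclusion.** A reader might infer that the plan rules out baseline glycemia. It does not. HbA1c and admission glucose are listed under Aim 3 as variables of interest, and the plan simply does not say how they enter the analysis. The larger gap is that no joint model with a group term is stated, and the covariates are part of specifying that model. This stands, and the fix starts there.
- **These are not baseline values of the outcome.** A reader might treat the omission as a missing baseline-outcome covariate. The outcome is daily percent of time, or of POC readings, in range, and no time in range before sensor placement is planned. HbA1c and admission glucose are predictors of it, of unknown strength.
- **Matching already does part of the work.** Diabetes type, home insulin, steroids and DKA/HHS status plausibly track starting glycemia. What matters is the r and g that remain, so the lower end of the ranges is more likely. At r = 0.3 and g = 0.1, type I error is only 5.5%.
- **The power loss is easily overstated.** A reader might say that the study is sized at exactly 80% and wastes power. That holds only at SD 25, which the plan offers as a high value. The Background reports SDs for time in range in the site's first 19 COVID-19 patients: 23 on day 1 and 16 on days 2-7. At SD 23, SE = 23 × 0.1414 = 3.25 and power is about 87%, rising to about 90% at r = 0.3. At SD 16, SE = 2.26 and power is 99.3%, rising to 99.6%.

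None of this removes the bias argument. Matching on correlates is not matching on the value, and the covariates named for RQ1 are not carried to RQ3.

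**Conclusion.** The concern holds as a matter of confounding control, with precision as a minor benefit. As written, RQ3 has no group term and no adjustment for starting glycemia, although the data for that adjustment are planned in both groups.

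The consequence runs from negligible to material: 0.5 points of bias and 5.2% type I error at r = 0.2 and g = 0.1, up to 3.75 points and 18.6% at r = 0.5 and g = 0.3, all at SD 25. A reader might take the upper figure as the design's false-positive rate. It is a conditional scenario resting on two assumptions that the documents do not supply.

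The stated power calculation is correct. Adjustment would not resolve a separate difficulty: CGM time in range is being set against the percentage of POC readings in range.

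**What to change.** In the RQ3 part of Data Analysis:

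1. Specify one joint linear mixed model for both groups, with a CGM-versus-control fixed effect, in place of a model for each group.
2. Prespecify HbA1c and admission glucose as fixed effects. Define the glucose as a value taken before CGM placement and, in controls, before an equivalent index time. Without that definition, the reading that qualified a control could also count as an outcome reading. The combined admission/inpatient glucose entry in Table 2 needs the same clarification.
3. Handle missing HbA1c by multiple imputation. A missing-value indicator can leave confounding among the patients who lack the test, which is the bias to be removed.
4. Report the adjusted difference as the main estimate, with the unadjusted one beside it.

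**Cost.** No extra patients or visits, and HbA1c and admission glucose are already on the data list. It is not purely a wording change, because the control index time must be defined and applied in the data extraction. Entry route (glucose threshold or IV insulin) is an optional further covariate. Table 2 does not list it, so it would have to be derived from the EHR.

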- No more than 1 episode of inappropriate insulin dose resulting in severe hypoglycemia (glucose <55mg/dl) after initial sensor validation
- No more than 1 episodes of iatrogenic DKA (pH <7.3 or serum bicarbonate <15 mEq/L in the setting of elevated ketones) or hyperosmolar nonketotic state (osmolality \geq 320mOsm/kg with BG >600mg/dl and pH >7.3 or serum bicarbonate >15 mEq/L)
- No episodes of severe adverse events resulting in prolonged hospitalization, or other life-threatening complication that attributed to the study intervention
- No severe adverse events resulting in death, or other life-threatening complication that is attributed to the study intervention
- No severe adverse event resulting in prolonged hospitalization, or other life-threatening complication that attributed to the study intervention and is expected to recur

Oversight and monitoring. Study team oversight of nursing use of the CGM system will be performed through a combination of (1) daily evaluation of EHR and CGM Clarity data and (2) through rounding on CGM patients (mon-Friday by PI ([name]), Co-I ([name]) and/or study coordinator (to be named) (Saturday, Sunday and holidays by the MICU charge nurse who will communicate that day with study team members. Daily rounds will allow the study team to continuously evaluate protocol fidelity and identify any safety concerns. The study staff will evaluate CGM use daily through Clarity CGM and EHR data to determine the following:

3. Was initial validation criteria achieved correctly and at what frequency
4. Is ongoing validations performed Q4 hours and according to validation criteria
5. If validation is met did the nurse begin hybrid use with non-adjunctive CGM use
6. Using clarity reports study staff will assess the presence of alarms (e.g., <100mg/dl, >300mg/dl, predictive hypoglycemia) Alarms will be reviewed daily by research staff to ensure hypoglycemia and hyperglycemia are being treated in accordance with OSUWMC guidelines.
7. Those patterns of hyperglycemia or hypoglycemia assessed every 24 hours, will be reported to primary team via pager/direct message to allow changes to insulin dosing as needed (e.g., max drip rate for IV insulin titration).
8. Assessment of change in clinical status criteria (Table 1) in which per protocol the nurse would increase frequency of POC testing and validation.

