The devices will be provided to OSU with permission to be used in this study by Dexcom LLC. They are stored at OSU College of Nursing in a locked office dedicated to the study research team. Accountability of devices used will be maintained in a device accountability log that includes device identification (transmitter serial number, sensor serial number, android phone serial number), patient ID; date of initial CGM device placement, date of sensor replacement (if applicable), date range for use. Transmitter, sensor, and phone serial numbers will be linked to participant/patient in the study. Dummy clinical Clarity accounts will be created for each device/patient. Android phone set-up requires entry of individual Dexcom Clarity account information on each phone. The patient's hospital identification label will be placed on the back of the Android phones once the device is placed to correctly match CGM device to the correct patient participant. CGM device orders from the manufacturer (Dexcom, LLC) will be tacked with date of receipt and shipping logs. Dexcom Expiration dates will be checked on initial receipt of items, monthly, prior to delivery to MICU, and prior to patient placement.

C. Adverse Events and Serious Adverse Events

Definition of Serious Adverse Events (SAE)

All temporal medical events will be tracked by the study team. An adverse event (AE) or suspected adverse reaction is considered "serious" if, in the view of either the investigator or sponsor, it results in any of the following outcomes: death, a life-threatening adverse event, prolongation of existing hospitalization or transfer to a more acute care environment, a persistent or significant incapacity or substantial disruption of the ability to conduct normal life functions. Important medical events that may not result in death, be life-threatening, or prolong hospitalization may be considered serious when, based upon appropriate medical judgment, they may jeopardize the participant and may require medical intervention to prevent one of the outcomes listed in this definition.

Severity of Event

- **Mild** – Events require minimal or no treatment and do not interfere with the participant's daily activities.
- **Moderate** – Events result in a low level of inconvenience or concern with the therapeutic measures. Moderate events may cause some interference with functioning.

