- **Severe** – Events interrupt a participant's usual daily activity and may require systemic drug therapy or other treatment. Severe events are usually potentially life-threatening or incapacitating. Of note, the term "severe" does not necessarily equate to "serious".]

Relationship to Study CGM

Potential adverse events (AEs) will be evaluated to determine their relationship to study intervention assessed by the clinician who examines and evaluates the participant based on temporal relationship and his/her clinical

judgment. The degree of certainty about causality will be graded using the categories below. In a clinical trial, the study product must always be suspect.

- **Related** – The AE is known to occur with the study intervention, there is a reasonable possibility that the study intervention caused the AE, or there is a temporal relationship between the study intervention and event. Reasonable possibility means that there is evidence to suggest a causal relationship between the study intervention and the AE.
- **Not Related** – There is not a reasonable possibility that the administration of the study intervention caused the event, there is no temporal relationship between the study intervention and event onset, or an alternate etiology has been established.

All AEs including local and systemic reactions not meeting the criteria for SAEs will be captured on the appropriate case report form (CRF). Information to be collected includes event description, time of onset, clinician's assessment of severity, relationship to study product (assessed only by those with the training and authority to make a diagnosis), and time of resolution/stabilization of the event. All AEs occurring while on study must be documented appropriately regardless of relationship. All AEs will be followed to adequate resolution.

Historically, few adverse events have been reported with Dexcom G6 CGM systems and have been isolated to mild skin irritation associated with the manufacturer's adhesive.⁴⁵

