An investigator shall submit to the sponsor and to the reviewing IRB a report of any unanticipated adverse device effect occurring during an investigation as soon as possible, but in no event later than 10 working days after the investigator first learns of the effect (21 CFR 812.150(a)(1)). A sponsor who conducts an evaluation of an unanticipated adverse device effect under 812.46(b) shall report the results of such evaluation to the FDA and to all reviewing IRB's and participating investigators within 10 working days after the sponsor first receives notice of the effect. Thereafter the sponsor shall submit such additional reports concerning the effect as FDA requests (21 CFR 812.150(b)(1)).

E. Study and individual participant stopping criteria:

We plan to enroll participants in waves of 20 with ongoing analysis between waves. We plan to stop the study for the following conditions in consultation with the data safety monitoring board assigned to oversee safety activities and the study:

- Failure to meet initial validation criteria within 24 hours in 20% of participants
- CGM-meter pairs obtained during routine monitoring following initial validation without a change in clinical status prompting hourly monitoring meeting the following criteria:
 - Failure to detect clinically significant hypoglycemia (≥ 2 episodes): CGM value >100 mg/dl with no Urgent Low Soon alert while POC BG <70 mg/dl
 - Failure to detect severe hyperglycemia (≥ 2 episodes): CGM value <180 mg/dl when POC BG >400 mg/dl
 - Inappropriate treatment (≥ 2 episodes): CGM value triggers the opposite action than the POC BG value (CGM >180 mg/dl while POC BG <70 mg/dl or vice versa).
- ≥ 2 episodes of inappropriate insulin dose resulting in clinically significant hypoglycemia (glucose <55 mg/dl) after initial sensor validation
- ≥ 2 episodes of iatrogenic DKA (pH <7.3 or serum bicarbonate <15 mEq/L in the setting of elevated ketones) or hyperosmolar nonketotic state (osmolality ≥ 320 mOsm/kg with BG >600 mg/dl and pH >7.3 or serum bicarbonate >15 mEq/L)
- ≥ 2 episodes severe adverse events resulting in prolonged hospitalization, or other life-threatening complication that are attributed to the study intervention
- Any severe adverse event resulting in death, or other life-threatening complication that is attributed to the study intervention

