- Any severe adverse event resulting in prolonged hospitalization, or other life-threatening complication that is attributed to the study intervention and is expected to recur

Patient participation in the study will stop if any of the following occur:

- Failed sensor validation x 2 sensors (48 hours)
- Transitioned to hospice care
- Patient participant or patient's legally authorized representative withdraw consent

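### Pilot benchmarks and stopping criteria count 'severe' adverse events, so read literally an attributed event that prolongs hospitalization but is graded moderate is serious yet triggers none of them

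*Combined protocol and SAP*

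**What the plan says.** **Stopping criteria (IV.E).** Three bullets concern adverse events in general. The first sets a limit of two or more episodes of "severe adverse events resulting in prolonged hospitalization, or other life-threatening complication that are attributed to the study intervention". The second is met by a single *severe* event, if attributed, that is fatal or threatens life. The third is also met by a single attributed *severe* event, where it lengthens the stay or threatens life and a recurrence is expected.

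**Pilot benchmarks (III.C, Staggered enrollment and initial pilot).** Three bullets mirror these. One reads "No episodes of severe adverse events resulting in prolonged hospitalization, or other life-threatening complication that attributed to the study intervention". A second covers fatal events and is worded "No severe adverse events resulting in death, or other life-threatening complication that is attributed to the study intervention". The third bars events that lengthen the stay or threaten life when they are expected to recur, and it too says *severe*. III.C makes meeting the benchmarks a condition of further enrollment.

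**Definitions (IV.C).** An event is serious by its outcome. The list includes death, threat to life and "prolongation of existing hospitalization or transfer to a more acute care environment", and no intensity grade is required. Mild, moderate and severe form a separate scale based on treatment needed and interference with activity. The text then cautions: "Of note, the term 'severe' does not necessarily equate to 'serious".

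**DSMB (IV.A).** Every serious event is reported to the DSMB, whatever its severity, attribution or expectedness. The DSMB may recommend continuing, modifying, suspending or terminating the study.

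**The concern.** The six bullets take their outcomes from the definition of *serious* but their adjective from the severity scale. Because IV.C tells the reader not to equate the two, a careful reader will treat *severe* as an additional condition. An attributed event that lengthens the stay then counts only if someone also grades it severe.

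At stake is whether a prespecified safety decision comes out the same way for every reader. Two people applying *severe* and *serious* to one moderate-graded event that prolonged a stay would disagree on whether the pilot had passed, and the pilot result decides whether enrollment goes on. The severity grades are also described by interference with daily activity, which is hard to apply to MICU patients. That last remark is an inference from the wording, since the documents say nothing about how reliable the grading is.

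**Working it through.** The plan states no figure on this point, so the check is a comparison of texts.

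**Step 1. What each bullet requires.**

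| Bullet | Grade | Outcome named | Other condition | Threshold |
|---|---|---|---|---|
| III.C, first | severe | prolonged stay or life-threatening | attributed | none allowed |
| III.C, second | severe | death or life-threatening | attributed | none allowed |
| III.C, third | severe | prolonged stay or life-threatening | attributed, expected to recur | none allowed |
| IV.E, first | severe | prolonged stay or life-threatening | attributed | two or more |
| IV.E, second | severe | death or life-threatening | attributed | any |
| IV.E, third | severe | prolonged stay or life-threatening | attributed, expected to recur | any |

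All six carry the grade, and four name prolonged hospitalization.

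**Step 2. A test case.** Take an attributed event that prolongs the stay, is not life-threatening, and is graded moderate.
- IV.C: serious, because prolongation is a listed outcome.
- IV.A: reported to the DSMB.
- Six bullets: not met, because the grade is not severe.

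Two such events make 2 serious events for reporting, 0 against the zero-tolerance pilot line and 0 toward the two-or-more stopping line.

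**Step 3. Where the gap is real.** Fatal or life-threatening events would nearly always be graded severe, since IV.C describes severe events as usually potentially life-threatening or incapacitating. For those outcomes the extra word changes little. In IV.E any single attributed life-threatening event already appears in the second bullet, so the two-or-more bullet does separate work only for prolonged stays. That is where the grade matters.

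**Step 4. Illustration of scale, on assumptions only.** The documents give neither the rate *r* of attributed, stay-prolonging events per patient nor the fraction *f* graded severe. Assume at most one event per patient, independence, and *p* = *r* × *f*.
- Pilot of 20: P(1 or more) = 1 − (1 − p)^20
- All 100 patients: P(2 or more) = 1 − (1 − p)^100 − 100p(1 − p)^99

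For *r* = 2%: with *f* = 1 the pilot figure is 1 − 0.98^20 = 33%; with *f* = 0.5 it is 1 − 0.99^20 = 18%.

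| Assumed r | Pilot, all count | Pilot, half graded severe | 2+ in 100, all count | 2+ in 100, half graded severe |
|---|---|---|---|---|
| 1% | 18% | 10% | 26% | 9% |
| 2% | 33% | 18% | 60% | 26% |
| 5% | 64% | 40% | 96% | 72% |
| 10% | 88% | 64% | >99% | 96% |

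With three quarters graded severe and *r* = 2%, the figures are 26% (pilot) and 44% (2 or more in 100). The table shows only that the adjective can matter if *f* is well below 1. It is not an estimate for this trial.

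**The case against.** The strongest reply is that this is loose wording with little practical effect. Several parts of it stand.

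- **The outcome is already in the rule.** Each bullet names a seriousness outcome and requires attribution, which suggests the authors meant *serious*. This is probably right, but the caution in IV.C points readers the other way.
- **The grades leave a narrow gap.** Moderate is described as a low level of inconvenience or concern, while severe covers events that may need systemic or other treatment. Most events that lengthen an ICU stay would fit severe better, and a mild event doing so is hard to imagine. This narrows the point without closing it, because nothing in IV.C excludes a moderate grade.
- **The foreseeable harms have their own rules.** Inappropriate dosing with glucose below 55 mg/dl, iatrogenic DKA and hyperosmolar state (III.C and IV.E), and missed or opposite-action readings (IV.E) are judged on glucose or laboratory values. They do not reach an attributed event outside those limits, such as a non-glycemic device complication.
- **The DSMB sees every serious event and can act.** The stopping criteria are themselves applied in consultation with it. That protection is discretionary, however. Scheduled meetings are at least every six months against an expected seven months of recruitment, though extra meetings are allowed. The pilot benchmarks are the fixed check.

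A reader might infer more: that the safety rules as a whole rest on the wrong attribute, or that serious harm could pass unseen or could not stop the study. The documents do not support this, for the reasons just given. Nor do they support a numerical claim. The background section reports no adverse events across the cited inpatient studies, and IV.C reports few with this device, limited to mild skin irritation.

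**Conclusion.** The point holds in a limited form. There is a genuine inconsistency between the six bullets and the definitions in IV.C. Its practical reach is mainly the prolonged-hospitalization limb of four bullets, for attributed events graded below severe. The conclusion rests on reading the terms as IV.C defines them. If the team reads *severe* as *serious*, the gap disappears in practice, but the text does not say so. Because the wording sits in a rule that decides whether enrollment continues, it is more than a clerical matter and should be corrected, although the mitigations keep it from being a major safety defect.

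**What to change.** Reconcile the adverse-event bullets in III.C and IV.E with the definitions in IV.C, and state in all six which defined term governs. If the intent is that the named outcome decides whether an event counts, with no added intensity grade, citing the IV.C definition of a serious adverse event in each bullet would achieve it. If a severity grade is meant as a further condition, the plan should say so and give the reason. The counts and thresholds remain for the sponsor and DSMB to set.

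The substitution would not bring every serious event into the rules. Events that are serious only through transfer to more acute care, incapacity or medical importance ("Important medical events that may not result in death, be life-threatening, or prolong hospitalization may be considered serious when" certain conditions are met) would still fall outside, because the bullets list only death, prolonged stay and life-threatening complications. The sponsor should confirm that this is intended.

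The cost is a small wording change in six places. Slightly more events may count toward the benchmarks and stopping rules, which makes a pause somewhat more likely.
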